## **8.7. Analysis of Safety**

### **8.7.1. Extent of Exposure and Compliance of Study Drug**

#### **8.7.1.1. Extent of Exposure**

The number of days that cream is applied will be summarized using descriptive statistics by treatment group and overall. Descriptive statistics will also be provided for duration of exposure days (number of days cream applied) into categorical summary of < 14, ≥ 14 to < 30, ≥ 30 to < 60, ≥ 60 to < 90, ≥ 90).

Extent of exposure will also be presented for subgroups of interest.

#### **8.7.1.2. Measurements of Treatment Compliance**

Percent compliance will be summarized using descriptive statistics (n, mean, standard deviation, median, minimum, maximum) for < 70%, ≥ 70%, and overall by treatment group.

### **8.7.2. Adverse Events by Preferred Term and System Organ Class**

Adverse events will be classified as treatment-emergent or non treatment-emergent.

A non-treatment emergent AE is defined as an AE that originated prior to the first dose of study drug and did not change in severity or relationship to treatment on or after the date of the first dose of study drug. If the severity or relationship to treatment changed on or after the first dose of study drug prior to the end of study, then that AE is considered a TEAE.

For subjects entering directly into extension study SD-006, there is no follow-up period after the last day on study. The safety information will be entered into SD-006 database. For subjects not entering the extension study the SD-006, the follow-up information will be captured in the source documents and will not be collected in the clinical database. Serious Adverse Events (SAEs) will be entered into the safety database.

### **8.7.3. Summaries of Adverse Event Incidence Rates for All Subjects**

The number and percentage of subjects who experienced TEAEs will be presented by system organ class (SOC) and by preferred term (PT) within SOC for each treatment group. TEAEs will be similarly presented by severity (mild, moderate, severe), by relationship to study drug (related would include definite, probable, and possible) and by outcome of events. Additionally, the number of TEAEs (as opposed to the number and percentage of subjects) will be presented by treatment group.

Analysis will also be done for subgroups of interest. Subgroups for age are defined based on the subject's age at Baseline. Details are provided in the appendices.

To count the number of subjects who experienced each TEAE, a subject experiencing the same TEAE multiple times will only be counted once for the corresponding PT. Similarly, if a subject experiences multiple TEAEs within the same SOC, the subject will be counted only once for that SOC. If a subject experiencing more than one TEAE within different severity or relationship categories within the same SOC/PT, only the worst case (worst severity and related TEAE) will be reported. TEAEs will be sorted alphabetically by SOC and within each SOC the PT will be presented by decreasing order of total frequency.

For TEAE summary by outcome, if a subject experienced more than one TEAE, the worst outcome will be counted under that subject. If a subject experienced more than one outcome within a SOC (or PT), the subject is only counted once under worst outcome in that SOC (or PT).

In addition, all adverse events will be provided by study site and by treatment group, in a listing, which will include the subject identifier, the PT, the reported term, the severity, the seriousness, the action taken, the outcome, the causality, the date onset, date of onset relative to the date of the first study drug administration, date of resolution, date of resolution related to the first study drug administration, and the TEAE duration (resolution date –onset date + 1). Separate listings will be provided for non-treatment emergent AEs, if any.

### **8.7.4. Missing AE Onset, Severity, and Relationship**

#### **8.7.4.1. Missing or Partial AE Dates**

The following list describes how partially missing date information will be handled as it relates to partial or missing start dates. Partial dates will be imputed as follows:

1. If year is not missing and is after the year of first application of study drug:

- a. If Month is missing, then Month will be imputed as January
- b. If Day is missing, then Day will be imputed as the first of the month
2. If year is not missing and is the same as the year of the first application of study drug:
  - a. If Month is missing, then impute the Month as the month of the first application of study drug
  - b. If Day is missing but Month is on or after the month of first application of study drug, then impute Day as the first day of study drug application
  - c. If Day is missing but Month is on or after the month of first application of study drug, then impute Day as the first day of - the month.
  - d. If the Day and Month are missing, then impute Day and Month as the Day and Month of the first study drug application.
3. If year is missing, then impute the year as the year of the first study drug application:
  - a. If Month is missing, then impute the Month as the Month of the first study drug application
  - b. If Day is missing, then impute the Day as the day of the first study drug application
4. If the start date is completely missing, but the AE is either ongoing or the stop date is after the first date of drug application, then impute the start date as the first date of study drug application.
5. If using the above rules, the stop date is before the start date, then leave the stop date missing and assume that AE is treatment emergent for the purpose of the analysis.

Completely missing stop dates will not be imputed. The partial stop dates will be imputed as follows:

1. If the year is missing, the stop date will not be imputed
2. If the month is missing, then the month will be imputed as December
3. If the day is missing, then the day will be imputed as the last day of the month

Imputed dates will be flagged in the individual supportive subject listings.

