11.3. Adverse Events

Adverse events (AEs) may be volunteered spontaneously by the patient or discovered as a result of general, non-leading questioning. All AEs should be recorded in the eCRF. Adverse events will be collected after signing the informed consent/assent through Visit 5 and these AEs will be followed up to 30 days after the last dose of study drug has been administered. This follow up is not required for subjects who enter the SD-006 study.

In the case of withdrawal due to an AE/SAE, the patient will be followed until resolution of the AE, or until in the opinion of the Investigator, the event has stabilized, or the Investigator does not expect any further improvement or worsening of the subject's condition, and the patient is referred to their primary physician for appropriate management of the ongoing event. Reasonable efforts will be made to contact a patient who fails to attend any follow-up appointments, in order to ensure that he/she is in satisfactory health.

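### A missing adverse-event onset year always becomes the first-dose year, so a known January to early-April onset after a late-year first dose is dated before treatment and usually leaves the TEAE tables

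*SAP*

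**What the plan says.** The rules for partial onset dates appear twice, in SAP 6.4.2 and 8.7.4.1. Rule 3 is the same in substance in both: "If year is missing, then impute the year as the year of the first study drug application". Its sub-rules replace the other parts only if those are missing too: "If Month is missing, then impute the Month as the Month of the first study drug application" and "If Day is missing, then impute the Day as the day of the first study drug application". A month that was recorded therefore stands.

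Two further rules might be expected to catch a bad result. Rule 4 begins "If the start date is completely missing, but the AE is either ongoing or the stop date is after the first date of drug application" and then assigns the first application date. Rule 5 applies when the stop date falls before the start date; it leaves the stop date missing and treats the event as treatment-emergent.

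SAP 8.7.2 classes as non-treatment-emergent "an AE that originated prior to the first dose of study drug", provided that its severity and relationship did not change on or after first dose. Protocol 11.3 sets the collection period: "Adverse events will be collected after signing the informed consent/assent through Visit 5". The schedule in Protocol 11 allows screening from Day -7 to Day 0 and places Visit 5 at Day 90 ±7.

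For partial stop dates, SAP 8.7.4.1 says "If the month is missing, then the month will be imputed as December", and a missing day becomes the last day of the month. The adverse-event listing in SAP 8.7.3 includes "the TEAE duration (resolution date –onset date + 1").

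**The concern.** Follow-up of about three months crosses 31 December for anyone first dosed late in the year. For these patients the first-dose year is the wrong year for every onset in January or later. Rule 3 then moves such an onset back by a full year, to a date well before consent, when the protocol was not collecting events.

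The result also runs against the rest of the list. If year, month and day are all missing, rule 3 gives the date of first application and the event counts as treatment-emergent. If the site managed to record the month, the event can drop out. Better information gives a worse classification, while rules 4 and 5 settle doubt in favour of treatment-emergent. What is at stake is the completeness of the TEAE summaries, the main safety tables.

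**Working it through.** The plan states no figure to reproduce here, so the check applies the rules to dates. First dose is taken as Day 0.

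**Does a known month fix the year?** The collection window runs from Day -7 to Day 97, a span of 104 days. It touches at most five calendar months, so no month name can occur in it twice. The year is determined.

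**Worked case.** First dose 1 December 2015, onset recorded as 15 January, year missing.
- Only admissible year: 2016, which is Day 45 (30 days to 31 December, plus 15).
- Rule 3 gives 15 January 2015, which is 365 - 45 = 320 days before first dose and 320 - 7 = 313 days before the earliest consent.
- Rule 4 does not apply, because the start date is not completely missing.
- Rule 5 does not apply. Moving the start a year too early cannot put it after the stop.
- SAP 8.7.2 then makes the event non-treatment-emergent, unless severity or relationship changed on or after first dose.

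**Further cases**

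| First dose | True onset | Imputed onset | Days before first dose |
|---|---|---|---|
| 15 Nov 2015 | 20 Jan 2016 | 20 Jan 2015 | 299 |
| 1 Dec 2015 | 10 Feb 2016 | 10 Feb 2015 | 294 |
| 15 Dec 2015 | 5 Mar 2016 | 5 Mar 2015 | 285 |

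If the day is missing as well, rule 3 inserts the first-dose day, and these become 304, 303 and 275 days before first dose.

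**Who is exposed.** With 90 days of follow-up, first doses from 3 October to 31 December, for onsets from January to 30 March. With 97 days, first doses from 26 September, for onsets up to 6 April. The shift places onset about 9 to 12 months before first dose (365 - 97 = 268 days at the short end, 365 - 1 = 364 at the long end).

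**Share of events.** Assume first doses spread evenly over 365 days and onsets evenly over Day 0 to Day F. For an onset on Day j, j of the 365 possible first-dose dates put it in the next calendar year. The misclassified share, among on-treatment events with a missing year and a known month, is

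sum of j for j = 0 to F, divided by 365(F + 1) = F / 730.

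- F = 83: 11.4%
- F = 90: 12.3%
- F = 97: 13.3%

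Enumerating every combination gave the same shares, before allowing for events kept by a change in severity or relationship. With the year restricted to the interval from consent to last visit, and month and day known, every onset had exactly one admissible year and none fell before first dose.

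**Opposite direction.** First dose 3 January 2016, pre-dose onset 29 December 2015, year missing. Rule 3 gives 29 December 2016, 361 days after first dose, and the event counts as treatment-emergent. This needs an onset inside the screening window of up to 7 days.

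**The case against.** The strongest reply is that this will hardly ever matter. Visits fall at about Days 14, 30, 60 and 90, data go into an eCRF and monitoring is regular, so a recorded month without a year is an unlikely entry. The rule treats both arms alike. An affected event is not lost: it appears in the non-treatment-emergent listing (16.2.7.2), a serious one stays in the all-SAE tables (14.3.1.13.1 and 14.3.1.13.2), and imputed dates are flagged in listings. A flagged onset 320 days before first dose would stand out. All of this stands and limits the size of the point. It does not make the rule right.

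Three stronger readings are tempting, and the documents do not support them.
- *About a quarter of patients are affected.* The figures 90/365 = 25% and 97/365 = 27% count patients whose first-dose date makes the error possible under even enrolment. Most of their onsets need not cross the year end, and the error also needs a missing year with a known month.
- *The event leaves every TEAE table, always in the direction that flatters safety.* SAP 6.4.2 and 8.7.2 keep an event whose severity or relationship changed on or after first dose, and the screening-window case runs the other way.
- *The uncapped stop dates are an equal fault.* With first dose 10 January 2016, a stop known only as 2016 becomes 31 December 2016, 259 days after Day 97. But the plan uses duration only as a listing column, and a late stop cannot remove an event from the TEAE tables. A late stop can also be real: Protocol 11.3 follows patients withdrawn for an adverse event until it resolves, stabilises or is not expected to change further.

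**Conclusion.** The point holds as a minor defect in rule 3 of SAP 6.4.2 and 8.7.4.1. When the year is missing and the month is known, the rule gives an impossible onset date for some patients first dosed from about October, and no other rule corrects it. The usual effect is that a true treatment-emergent event moves to the non-treatment-emergent listing.

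The size is about 12% to 13% of on-treatment events with that pattern of missing parts. This rests on even enrolment over the year, even onset over 90 to 97 days, and first dose on Day 0; the documents give neither distribution. They also give no count of such events, which may be zero. Nothing here suggests that the overall safety picture would change. Stop-date imputation is a remark only.

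**What to change.** Add the following to rule 3 in both SAP 6.4.2 and 8.7.4.1: when the year is missing and the month is known, use the year that places onset between informed consent and the end of adverse-event collection (Visit 5 or early termination). If this still leaves treatment emergence undetermined, count the event as treatment-emergent.

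The cost is two sentences, identical in both sections, and a bound in the date-imputation code. Since the SAP amendment includes changes made after database lock, first run one query for adverse events with a missing onset year. If there are none, no table changes and the amendment is for the record only.

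If stop dates are bounded as well, the limit should be the patient's actual last recorded contact, including any extended follow-up under Protocol 11.3. A fixed Day 90 or 30-day limit would cut off real resolution dates.

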#### **6.4.2. Treatment-emergent Adverse Events**

Treatment-emergent AEs (TEAEs) are undesirable experiences, signs, or symptoms that begin or change in severity or relationship to treatment at the time of or after the first administration of study drug prior to the end of study.

The investigator's verbatim term of both serious and non-serious AEs will be mapped to system organ class (SOC) and preferred terms (PTs) using the 19.1 version of the Medical Dictionary for Regulatory Activities (MedDRA). Partial dates will be imputed as the following:

1. If year is not missing and is after the year of first application of study drug:
  - a. If Month is missing, then Month will be imputed as January
  - b. If Day is missing, then Day will be imputed as the first of the month
2. If year is not missing and is the same as the year of the first application of study drug:
  - a. If Month is missing, then impute the Month as the month of the first application of study drug
  - b. If Day is missing but Month is on or after the month of first application of study drug, then impute Day as the first day of study drug application
3. If year is missing, then impute the year as the year of the first study drug application:
  - a. If Month is missing, then impute the Month as the Month of the first drug application
  - b. If Day is missing, then impute the Day as the day of the first study drug application.
4. If the start date is completely missing, but the AE is either ongoing or the stop date is after the first date of drug application, then impute the start date as the first date of drug application.
5. If using the above rules, the stop date is before the start date, then leave the stop date missing and assume that AE is treatment emergent for the purpose of the analysis.

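### The adverse event date rules can count an event that ended before the first application as treatment-emergent, because rule 5 drops a conflicting stop date without checking it against first application

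*SAP*

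**What the plan says.** The rules for incomplete start dates appear twice in the SAP, in Sections 6.4.2 and 8.7.4.1. Where the year is that of first application:

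- **Month missing (2a, both sections):** the month of first application is used.
- **Day missing, month on or after that of first application (2b, both sections):** "then impute Day as the first day of study drug application".
- **The same condition (2c, 8.7.4.1 only):** "then impute Day as the first day of - the month".
- **Day and month missing (2d, 8.7.4.1 only):** "If the Day and Month are missing, then impute Day and Month as the Day and Month of the first study drug application".

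Rule 3 begins "If year is missing, then impute the year as the year of the first study drug application" and fills a missing month and day from first application too. Rule 4 covers a completely missing start. It imputes the first application date only if the event is ongoing or its stop falls after first application.

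Rule 5 covers a conflict after imputation. In 8.7.4.1 it says that if "the stop date is before the start date, then leave the stop date missing and assume that AE is treatment emergent". Section 6.4.2 has the same rule: "leave the stop date missing and assume that AE is treatment emergent for the purpose of the analysis". Neither version makes an exception for a stop before first application.

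Section 8.7.2 defines an event as not treatment-emergent if it arose before the first dose and its severity and relationship did not change from that dose onward. Protocol 11.3 lets such events into the database: "Adverse events will be collected after signing the informed consent/assent through Visit 5".

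**The concern.** Rule 5 needs a stop date to work on. When that stop precedes an imputed start, at least one of the two dates is wrong, and the imputed one is the obvious suspect. The rule keeps the imputed date and discards the other.

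Treating an event as emergent is a sensible default when its timing is unknown. It is not sensible when the stop date shows that the event was over before any cream was applied. Such an event must have begun before first application and cannot have changed after it, so it meets the 8.7.2 definition of not treatment-emergent.

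Two things are at stake: pre-treatment events entering the treatment-emergent tables, and on-treatment events losing a valid resolution date and hence the duration that 8.7.3 promises in the listing.

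**Working it through.** The plan states no figure here, so the check applies the rules literally.

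**Worked case.** First application is 20 May and the recorded stop is 17 May of the same year.

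| Start as recorded | Rule | Imputed start | Stop before it? | Result as written |
|---|---|---|---|---|
| Year only | 2d (8.7.4.1); 2a then 2b (6.4.2) | 20 May | Yes | Stop dropped, treatment-emergent |
| May, day missing | 2b | 20 May | Yes | Stop dropped, treatment-emergent |
| May, day missing | 2c (8.7.4.1 only) | 1 May | No | Stop kept, not treatment-emergent |
| Nothing recorded | 3, read literally | 20 May | Yes | Stop dropped, treatment-emergent |
| Nothing recorded | 4 | None imputed | Not applicable | Rule 5 does not fire |

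Under 8.7.2 the event is not treatment-emergent in any row. The year-only row does not depend on how 2b and 2c are reconciled. The day-missing rows do.

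**Grid check of the logic.** Take events that start and end within Days -7 to -1, with an exact stop date. There are 7 + 6 + 5 + 4 + 3 + 2 + 1 = 28 start-stop pairs. Over 365 consecutive first-application dates this gives 28 × 365 = 10,220 combinations. The uniform grid is an assumption used to trace the rules; it does not predict frequency.

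| Missing parts of start | Called treatment-emergent as written | With the stop checked first |
|---|---|---|
| Day and month | 10,080 / 10,220 = 98.6% | 0 |
| Day, under 2b | 8,540 / 10,220 = 83.6% | 0 |
| Day, under 2c | 0 | 0 |
| All, under rule 3 | 10,220 / 10,220 = 100% | 0 |
| All, under rule 4 | 0 | 0 |

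The remainders, 10,220 − 10,080 = 140 and 10,220 − 8,540 = 1,680, are starts in an earlier year or in an earlier month. No imputation rule covers these.

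**Side effect under 2b.** Keep first application on 20 May. Let the start be recorded as June with the day missing, and the stop as 10 June. Rule 2b gives 20 June, so rule 5 drops the 10 June stop. The treatment-emergent label is right, but duration (resolution date − onset date + 1) can no longer be computed. Under 2c the start is 1 June and nothing is lost.

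A second grid used 270 first-application dates, onsets on Days 0 to 90, and assumed durations of 3, 7 and 14 days: 270 × 91 × 3 = 73,710 combinations. With the day missing and 2b applied, 21,399 lost a valid stop (29.0%). That share depends on the assumed durations.

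**Size per event.** With the planned 75 patients per arm, 1/75 = 1.3 percentage points. This is a maximum, because 8.7.3 counts a subject once per preferred term and once per system organ class.

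**The case against.** The strongest reply is that rule 2c prevents the problem. It does so only when just the day is missing, and only if 2c overrides 2b. Section 8.7.4.1 does not say which prevails, and 6.4.2 does not contain 2c. With day and month missing, 2c does not help.

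A second reply is that the impact is close to nil. Screening and baseline form one visit spanning Days -7 to 0, and the first dose is given at that visit upon randomization, so the pre-dose window may be zero for many patients. The Protocol's schedule marks adverse event monitoring only at Visits 2 to 5, although Protocol 11.3 requires collection from consent. A record must begin and end in that window, have a stop date and lack part of its start date. The rule is the same in both arms and errs toward counting. All of this stands, and it limits the size of the point. It does not make the classification correct.

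A third reply is that rule 5 may be aimed at imputed stop dates. That does not rescue it. Section 8.7.4.1 fills a partial stop with its latest possible date, so if even that precedes first application, the event was over.

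Some stronger readings are tempting but unsupported:

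- **All pre-dose events with partial starts are misclassified.** Rule 2c and rule 4 each give routes with no error, and a 100% rate among records on which rule 5 fires with a pre-dose stop is true by construction.
- **Rule 5 flatly contradicts rule 4.** They differ in approach but govern different cases.
- **Recorded data are destroyed.** The rule is an analysis derivation, and nothing in it alters source records.

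**Conclusion.** The point holds as an error in a stated derivation rule. An event that ended before first application is counted as treatment-emergent, contrary to 8.7.2, when the start day and month are missing, or when only the day is missing and 2b is used. For day-missing starts, 8.7.4.1 is undetermined until 2b and 2c are reconciled. Under 2b, on-treatment events in later months can also lose a valid stop date.

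The effect is probably small. The documents give no count of affected records, so this judgement rests on the window of at most 7 days and the need for an incomplete start date. Each false event moves an arm's incidence by at most 1.3 points. A reader might infer that the rule hides harm or affects the efficacy result. It does neither: it adds events, and it touches only safety output, which Section 7.1 treats as descriptive. The correction is nonetheless worth making because it is cheap and the present rule gives a wrong answer from known dates.

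**What to change.** Amend 6.4.2 and 8.7.4.1 identically:

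1. **Check the stop first.** If a complete stop date, or the latest possible date of a partial one, is before first application, keep it, classify the event as not treatment-emergent, and impute no start later than the stop.
2. **Reconcile 2b and 2c.** Apply 2b when the recorded month is the month of first application, and 2c when it is later.
3. **Resolve any remaining conflict in favour of the observed stop.** Cap the imputed start at the stop date, and flag the start and duration as imputed, since capping can create an artificial one-day duration. Steps 1 and 2 should leave few such records.

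Because the change follows database lock, list every record on which the present rule 5 fires and report treatment-emergent counts under both rules.

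The cost is a few sentences in two SAP sections, a modest change to the date derivation program, a short listing and a rerun of the adverse event tables. No new data are needed.
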